Most side effects associated with CDX-1140 have occurred in the 24-48 hours following the CDX-1140 infusion, consisted of infusion reactions/cytokine release syndromes, have been mild to moderate in severity, and have resolved with or without medications such as acetaminophen, NSAIDS, and/or anti-nausea medication. In a few cases, the side effects have been severe and have required hospitalization and treatment with corticosteroids or other immunosuppressive medications. Treatment related adverse events that have occurred in > 10% of patients are as follows: fatigue, joint pain, nausea, chills, fever, diarrhea, muscle pain, vomiting. Transient (usually low-grade) increases in liver transaminases have been seen in some patients, but no patient has had to discontinue therapy because of increased liver function tests. Cytokine release syndrome (including symptoms of fever, hypotension, hypoxia, fatigue, headache, and nausea) and pneumonitis have been the most common SAEs reported. Thus far, CDX-301 does not seem to add to the side effect profile of CDX-1140. The CDX-1140 Investigator Brochure provides additional details.

Our recommended phase II dose levels come from a phase I clinical trial that has established a MTD for CDX-1140 (Study CDX1140-01), as well as previous studies that have studied the MTD for CDX-301. These studies show the majority of potential toxicity comes CDX-1140, consistent with the mechanism of action of each drug.

CDX-1140 is being studied in one clinical trial. The first in human (FIH) trial (Study CDX1140-01) is an open-label, non-randomized, multicenter, dose-escalation study with expansion cohorts to evaluate the safety, tolerability, pharmacokinetics, pharmacodynamic, and clinical activity of intravenous CDX-1140 as a monotherapy and in combination with subcutaneous CDX-301 (Flt3L) in patients with advanced solid tumors and hematologic malignancies.

As of a cut-off date of 9/5/2019, a total of 58 patients have been treated; 41 with CDX-1140 monotherapy and 17 patients with CDX-1140 plus CDX-301 combination therapy. The Maximum Tolerated Dose (MTD) and recommended dose and administration schedule for CDX-1140 monotherapy has been defined as 1.5mg/kg every four weeks.

CDX-301 and CDX-1140 had been used previously, alone and in combination, at the doses we are giving without grade 3 or higher AEs. The combination has also been used safely in a dose escalation trial NCT03329950. Few of these prior studies incorporated pancreatic cancer patients, which is why the first six patients on our study will be treated as phase I and assessed for potential toxicity.

Initial studies examined the tolerability of CDX-301 alone. Using a standard 3+3 dose-escalating design, sequential cohorts of 3–6 healthy volunteers received CDX-301 by daily SC injection at a dose level of 1, 3, 10, 25 or 75 µg/kg for 5 days (Cohorts 1–5), 25 µg/kg for 7 days (Cohort 6) or 25 µg/kg for 10 days (Cohort 7). Transient lymphadenopathy (Grade 1) was seen in six subjects (25 or 75 µg/kg/day cohorts) and single cases of diarrhea, injection site erythema, folliculitis and dry mouth (all Grade 1) were observed. A single subject receiving CDX-301 at 75 µg/kg/day for 5 days developed community-acquired pneumonia on day 12. No other AE's were seen.

CDX-301 was given in a subsequent study (25 μ g/kg) with a lower dose of RT (2 Gy x 2) and another immune therapy without toxicity in lymphoma patients (Hammerich et al, Nat Med 2019).

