APPENDIX C: Reporting Timelines	

SCHEDULE OF ACTIVITIES

Arm 1 Calendar

	Screening ³	7-12 days prior to surgery	Surgery	Follow-up ⁴
7.0	**	to surgery		
Informed consent	X			
ECOG PS	X		X^7	
CBC w/diff	X			
CMP	X			
INR, aPTT	X			
Pregnancy test ¹	X			
Randomization	X^2			
CDX-1140		X		
Research blood	X	X ⁵	X	
Research tissue			X	
AE assessment ⁶		X	$X^{7,8}$	X
Progression and	_		_	X
survival				

- 1. For female patients of childbearing potential only.
- 2. After confirmation of eligibility.
- 3. Screening should occur no more than 6 weeks prior to surgery, CBC within 3 weeks prior to start of CDX-1140.
- 4. Follow-up will occur at standard of care office visits (approx. Q6M) for 24 months after surgery.
- 5. Prior to CDX1140 administration.
- 6. AEs will be collected from time of administration of CDX-1140 until surgery, or until 60 days after end of treatment if surgery doesn't take place. A phone call or medical record check may take place at the 60 day time point (+/- 2 weeks) for AE collection if surgery doesn't take place.
- 7. Follow-up in person visit or call with physician's office will occur 24-48 hours after administration of CDX-1140 to evaluate any acute changes.
- 8. Assessment of AEs may be done at an outpatient visit 7 +/- 2 days after administration of CDX-1140 or after admission for surgery.

Arm 2 Calendar

	Screening ⁵	D1	D2	D3	D4	D5	D8 ¹⁰	Surgery ³	Follow- up ⁶
Informed consent	X								•
ECOG PS	X							X^8	
CBC w/diff	X								
CMP	X								
INR, aPTT	X								
Pregnancy test ¹	X								
Randomization	X^2								
CDX-1140							X		
CDX-301		X	X	X	X	X			
Research blood	X^4						X^4	X^4	
Research tissue								X	
AE assessment			X -					X ^{7,8,9}	X^7
Progression and survival									X

- 1. For female patients of childbearing potential only.
- 2. After confirmation of eligibility.
- 3. 7-12 days after administration of CDX-1140.
- 4. First research blood draw will take place at screening or at any point prior to the first dose of CDX-301, second on day 8 prior to CDX1140 administration, and third at time of surgery.
- 5. Screening should occur no more than 6 weeks prior to surgery, CBC within 3 weeks prior to start of CDX-1140.
- 6. Follow-up will occur at standard of care office visits (approx. Q6M) for 24 months after surgery.

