1.4 Risk/Benefit Assessment

1.4.1 Known Potential Risks

Evidence from mouse and human tolerability studies suggest the study drugs, at the doses we are using, have a safety profile supportive of its further development as an anti-cancer therapeutic.

Treatment related adverse events that have occurred in > 10% of patients are as follows: fatigue, joint pain, nausea, chills, fever, diarrhea, muscle pain, and vomiting. Transient changes in liver function tests, platelet count, and lymphocyte count have been observed with CDX-1140. Transient increases in liver transaminases are expected in the 24-48 hours following the administration of CDX-1140. These changes have been mostly low grade and typically return to baseline within 1-2 week after the infusion. Important observed risks include cytokine release syndrome and pneumonitis. SQ and IV injections may lead to local discomfort or pain, and in some cases, infection.

[figure not shown]

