5 TREATMENT PLAN

5.1 Premedication Administration

5.1.1 CDX-1140

Prophylactic premedication is required for all patients: diphenhydramine 25/50 mg (or equivalent anti-histamine), 500 to 750 mg paracetamol (acetaminophen), and naproxen sodium 250 mg (or equivalent NSAID) at least 30 minutes prior to CDX-1140 administrations. Ranitidine 150 mg (or equivalent) may also be incorporated into the premedication regimen. Prophylactic premedication with corticosteroids

is to be avoided because of the potential to attenuate the anti-tumor activity of CDX-1140.

CDX-1140 will be administered intravenously over 90 minutes using a 0.22 micron in-line filter.

CDX-1140 post-infusion medication is also required for all patients. In the 24-48 hours following the CDX-1140 infusion, alternate oral acetaminophen (1000 mg) and non-steroidal anti-inflammatory (e.g., ibuprofen 200 mg) q6H. An anti-histamine and anti-emetic may also be utilized if clinically indicated. Patients should be evaluated to determine if continuation of post-infusion medication is needed on the day after CDX-1140 dosing. Note that the potential for toxicity with these drugs and appropriate precaution should be utilized in patients with risk factors for toxicity, e.g. patients with peptic ulcers, increased LFTs, or increased creatinine. Also, care should be taken to medicate for no longer than is necessary in order to avoid potential confounding factors in determining adverse event causality (e.g. increased LFTs).

All patients should be monitored for 4 to 6 hours post administration of CDX-1140 with standard post-infusion monitoring.

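### Section 5.9 can halt the trial on laboratory abnormalities, yet CBC and CMP are scheduled at screening only; separately, no operative section carries out the six-patient phase I step in 1.3.2

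*Combined protocol and SAP*

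**What the plan says.** Section 1.3.2 notes that few pancreatic cancer patients took part in the earlier studies and, for that reason, states that "the first six patients on our study will be treated as phase I and assessed for potential toxicity".

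Section 5.9 sets halts for the whole trial: one probably or definitely related Grade 3-4 event, one such SAE, or two patients with the same related event of Grade 2 or higher. The third criterion names laboratory abnormalities alongside cytokine release, infusion reactions and other clinical events. Arthralgia and myalgia adequately treated with a short steroid course are exempt under the first and third criteria.

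Section 1.4.1 reports transient changes in liver function tests, platelets and lymphocytes with CDX-1140. It adds: "Transient increases in liver transaminases are expected in the 24-48 hours following the administration of CDX-1140". On severity and duration it says: "These changes have been mostly low grade and typically return to baseline within 1-2 week after the infusion".

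In the Schedule of Activities, CBC, CMP and INR/aPTT each have one entry per calendar, at screening. The timing footnote reads: "Screening should occur no more than 6 weeks prior to surgery, CBC within 3 weeks prior to start of CDX-1140". After dosing, the calendars give a "Follow-up in person visit or call" at 24-48 hours, and state: "Assessment of AEs may be done at an outpatient visit 7 +/- 2 days after administration of CDX-1140 or after admission for surgery". The later scheduled blood draws are research blood, which section 9.3 assigns to PBMCs, plasma and sera.

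Section 5.1.1 covers the immediate period clinically: "All patients should be monitored for 4 to 6 hours post administration of CDX-1140 with standard post-infusion monitoring". It also requires acetaminophen and an NSAID after every infusion, advises precaution in patients with raised liver tests or creatinine, and warns that these drugs can obscure the cause of a raised liver test.

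**The concern.** A halt rule works only on what is observed. Criterion 3 relies in part on laboratory findings, and the drug has known laboratory effects, but the protocol schedules no test that would show them. Such an abnormality would enter the rule, and the by-arm safety summary, only through a test that the protocol does not require. Detection could then differ between patients and arms for reasons unrelated to treatment.

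Timing matters because the next event is a pancreatic resection. A change that takes one to two weeks to resolve may still be present when surgery falls 7-12 days after CDX-1140. Attribution matters too: criterion 3 counts only events judged probably or definitely related, and that judgement is harder without a recent pre-infusion value, given the mandatory acetaminophen and NSAID.

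The six-patient sentence is a separate matter. It describes a safeguard that a reader or ethics board might rely on, and the operative sections do not provide it.

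**Working it through.** The plan gives no figure for this point, so there is none to reproduce. The sample size and power in section 13.2 are not affected. The check sets the schedule against the halt rule and works out the intervals.

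**Interval without a scheduled safety test, first dose to surgery**

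- CDX-1140 arm: surgery is 7-12 days after the single infusion, so 7-12 days.
- Combination arm: CDX-1140 is on day 8 +/- 1 (Synopsis and calendar), which is 6-8 days after day 1. Adding 7-12 days gives 6 + 7 = 13 to 8 + 12 = 20 days.
- CBC, CMP or INR/aPTT entries in these intervals: none in either calendar.

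**Age of the last required CMP at the CDX-1140 infusion**

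- Screening may be up to 6 weeks = 42 days before surgery.
- The infusion is 7-12 days before surgery.
- Maximum age: 42 - 12 = 30 to 42 - 7 = 35 days. The CBC has a tighter limit of 3 weeks before CDX-1140; the CMP has none.

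**Overlap of expected changes with surgery**

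- Return to baseline in 1-2 weeks is 7-14 days after infusion, and surgery is on days 7-12. The two windows overlap throughout the surgical window.

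**The six-patient step**

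- 4.6: 1:1 randomization to 12 evaluable patients per arm, with no stage or pause.
- 5.3: no evaluability definition for a phase I group.
- 5.9: halts for the whole trial, with no reference to six patients.
- 12: semi-annual reports, with no review after patient six.
- 13: a two-arm randomized phase II design, with toxicity data collected by arm and no analysis of the first six.

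None of these defines a dose-limiting toxicity, an observation window or a decision for the six. The schema figure and some pages were not available in the text reviewed, so this holds for the supplied sections only.

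**Possible cost of testing: criterion 3 halts**

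This sizes a downside of the fix; it does not measure the gap. Let p be the chance that a patient has a given related Grade 2 or higher laboratory event. The chance that at least two of 24 patients have it is 1 - (1-p)^24 - 24p(1-p)^23. The protocol gives no value of p, so these are assumptions: p = 2% gives 8%, 5% gives 34%, 10% gives 71% and 20% gives 97%.

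**The case against.** The strongest reply is that the trial is already closely watched. Section 5.9 halts on a single related Grade 3-4 event (apart from the arthralgia and myalgia exemption) or a single related SAE from the first patient, with prompt notice to the QASMC. Patients are observed after infusion, contacted at 24-48 hours and assessed again before surgery. Section 5.4 asks for serum at an infusion reaction. Section 7.1.3 counts an abnormal laboratory finding as an adverse event, so a result from routine care would be recorded. Section 1.3.2 says that transaminase rises were usually low grade and that no patient stopped therapy because of them. CDX-1140 is given once, so a later result cannot change that patient's CDX-1140 dose.

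All of this stands, and it rules out several stronger readings that a reader might infer:

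- That the first six patients are unmonitored. They are covered by 5.9; what is absent is a distinct phase I step.
- That the halt rules do not work. The clinical triggers need no scheduled blood test; only the laboratory part of criterion 3 lacks a scheduled input.
- That the precaution in 5.1.1 has no liver or creatinine values behind it. The screening CMP and the eligibility limits in section 3.1 supply a baseline; only an updated value is missing.
- That severe laboratory toxicity should be expected. The documents describe mostly low-grade, transient changes.
- That no blood will in fact be tested before surgery. The documents are silent on routine pre-operative testing.

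What the reply does not supply is a scheduled post-dose CBC or CMP. Serum at an infusion reaction is event-driven, and recording incidental results is not systematic ascertainment by arm. Post-infusion results can still bear on surgery, supportive care and trial-level halts.

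**Conclusion.** The point holds in a limited form. Between first dose and surgery the protocol schedules no safety blood test, for 7-12 days in the CDX-1140 arm and 13-20 days in the combination arm, although criterion 3 of 5.9 counts laboratory abnormalities and 1.4.1 anticipates them. The last required CMP can be 30-35 days old at infusion. These intervals follow from the stated visit windows and need no assumption about event rates. No rate of missed or severe events can be derived from the documents, and none is claimed.

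The six-patient sentence in 1.3.2 is an unimplemented statement in a background section. It should be corrected, but because 5.9 applies from patient one it is mainly an inconsistency. Both parts are worth an amendment, and neither affects the primary analysis.

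**What to change.** 1. Add CBC with differential and CMP to both calendars at two existing contacts: the research draw before CDX-1140, and the adverse event assessment at day 7 +/- 2 or surgical admission, with results available before surgery. The first set updates the baseline in the CDX-1140 arm; in the combination arm it also gives a value after CDX-301.
2. Either delete the six-patient sentence in 1.3.2 and state that safety monitoring relies on 5.9, or have the QASMC review toxicity by arm once the sixth treated patient reaches surgery. If the review is chosen, it will carry limited information: no events in six patients leaves a one-sided 95% upper bound of 1 - 0.05^(1/6) = 39%, and no events in three (about half of six under 1:1 allocation) leaves 1 - 0.05^(1/3) = 63%.

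The cost is a protocol amendment and about 2 x 24 = 48 CBC/CMP sets, more if non-evaluable patients are replaced, with no new visits. The review option adds one QASMC look. Systematic testing may also produce more criterion 3 halts. Whether to exempt expected transient Grade 2 AST/ALT rises, as 5.9 already does for treated arthralgia and myalgia, is the sponsor's decision, since an exemption loosens a stopping rule. A brief rise at 24-48 hours may still be missed, because that contact can be a call.

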1.3.3 Scientific Rationale for Study Design

The key questions for these CDX-1140 and CDX-301 as anti-cancer agents in PDAC patients is what exactly their effects are on tumor infiltrating immune cells. While significant pre-clinical and modest clinical data are already present for both agents; Without fully understanding their effects in human PDAC tissues it is

difficult to predict the optimum ways to employ these agents. In this study for our primary endpoint of changes in intratumoral cDCs we will compare to historical tissues and analysis of untreated PDAC patients. Thus, here-in we will simply run two arms testing CDX-1140 alone and CDX-301 plus CDX-1140.

1.4 Risk/Benefit Assessment

1.4.1 Known Potential Risks

Evidence from mouse and human tolerability studies suggest the study drugs, at the doses we are using, have a safety profile supportive of its further development as an anti-cancer therapeutic.

Treatment related adverse events that have occurred in > 10% of patients are as follows: fatigue, joint pain, nausea, chills, fever, diarrhea, muscle pain, and vomiting. Transient changes in liver function tests, platelet count, and lymphocyte count have been observed with CDX-1140. Transient increases in liver transaminases are expected in the 24-48 hours following the administration of CDX-1140. These changes have been mostly low grade and typically return to baseline within 1-2 week after the infusion. Important observed risks include cytokine release syndrome and pneumonitis. SQ and IV injections may lead to local discomfort or pain, and in some cases, infection.

[figure not shown]

1.4.3 Assessment of Potential Risks and Benefits

The benefit-risk assessment of CDX-1140 with CDX-301 should be taken in the context of a drug in the early stages of development, and therefore is by definition uncertain and evolving. In the early clinical experience to date, this therapy has demonstrated an acceptable toxicity profile with evidence of biologic and clinical activity consistent with the mechanism of action.

In the best-case scenario, and that predicted by prior animal studies, the potential benefit of this therapy is tumor regression. In a population of patients that is overwhelmingly incurable, the potential risk benefit ratio appears very favorable.

3 STUDY POPULATION

3.1 Inclusion Criteria

- 1. Histologically or cytologically confirmed surgically resectable pancreatic ductal adenocarcinoma, but not adenosquamous/squamous pancreas cancers (as determined by operating surgeon or tumor board). Patients who have previously received chemotherapy for his/her pancreas cancer within the past 6 months and who are now deemed resectable are also eligible for this trial.
- 2. At least 18 years of age.
- 3. ECOG performance status ≤ 1 (see Appendix A)
- 4. Normal bone marrow and organ function as defined below:
 - a. Absolute neutrophil count $\geq 1,500$ /cumm
 - b. Platelets > 100,000 /cumm
 - c. Hemoglobin $\geq 9.0 \text{ g/dL}$
 - d. $AST(SGOT)/ALT(SGPT) \le 2.5 \times IULN$
 - e. Creatinine clearance ≤ 1.5 x IULN or glomerular filtration rate of ≥ 60 mL/min
 - f. INR \leq 1.5 x IULN unless patient is receiving anticoagulant therapy as long as INR or PTT is within therapeutic range of intended use of anticoagulants
 - g. $aPTT \le 1.5 \times IULN$ unless patient is receiving anticoagulant therapy as long as INR or PTT is within therapeutic range of intended use of anticoagulants
 - h. Albumin $\geq 3.0 \text{mg/dL}$
- 5. The effects of CDX-301 and CDX-1140 on the developing human fetus are unknown. For this reason, women of childbearing potential and men must agree to use adequate contraception (hormonal or barrier method of birth control, abstinence) prior to study entry, for the duration of study participation, and for 3 months after the last dose of either study drug. Should a woman become pregnant or suspect she is pregnant while participating in this study or for 3 months after the last dose of either study drug, she must inform her treating physician immediately.

6. Ability to understand and willingness to sign an IRB approved written informed consent document (or that of legally authorized representative, if applicable).

3.2 Exclusion Criteria

- 1. Immmune deficienties such as HIV.
- 2. A history of other malignancy with the exception of malignancies for which all treatment was completed at least 2 years before registration and the patient has no evidence of disease.
- 3. Currently receiving any other investigational agents or has received any other investigational agents within 4 weeks or 5 half-lives of the planned first dose of study treatment.
- 4. Receipt of chemotherapy within 2 weeks of planned first dose of study treatment.
- 5. A history of allergic reactions attributed to compounds of similar chemical or biologic composition to CDX-301 or CDX-1140 or other agents used in the study.
- 6. Has a diagnosis of immunodeficiency or is receiving chronic systemic steroid therapy (for > 1 month of 10 mg prednisone daily, or equivalent) or any other form of immunosuppressive therapy not routinely associated with chemotherapeutic regimen.
- 7. Uncontrolled intercurrent illness including, but not limited to, ongoing or active infection, symptomatic congestive heart failure, unstable angina pectoris, cardiac arrhythmia, immunosuppression, autoimmune conditions, or underlying pulmonary disease.
- 8. Uncontrolled intercurrent illness including, but not limited to, ongoing or active infection, immunosuppression, autoimmune conditions, or underlying pulmonary disease.
- 9. Has an autoimmune disease requiring systemic treatment within the past 2 years (i.e. with use of disease modifying agents, corticosteroids, or immunosuppressive drugs). Replacement therapy (e.g., thyroxine, insulin, or physiologic corticosteroid replacement therapy for adrenal or pituitary insufficiency, etc.) is not considered a form of systemic treatment.
- 10. Known history of hepatitis B (defined as hepatitis B surface antigen [HBsAg] reactive) or known active hepatitis C virus (defined as HCV RNA [qualitative] is detected).
- 11. Has a history of (non-infectious) pneumonitis that required steroids or current pneumonitis.
- 12. Has a known history of active TB (bacillus tuberculosis).

- 13. Major surgery within 28 days prior to the first study treatment.
- 14. Pregnant and/or breastfeeding. Women of childbearing potential must have a negative pregnancy test within 14 days of study entry.
- 15. History of bone marrow or solid organ transplant.
- 16. Patients with a history of myocardial infarction, cerebral vascular accident, thrombosis or pulmonary embolus within 12 months prior to the first dose of study treatment are excluded from this study.
- 17. Patients with known mutations/amplifications in Flt3

